14.5.3 Body Mass Index

Weight (kg) and standing height are collected at Screening, Day 1, Week 13, Week 26, Week 39, and Week 52.

Body Mass Index (BMI) will be calculated at each visit as:

$$\text{Body Mass Index (kg/m}^2\text{)} = \frac{\text{Weight (kg)}}{\text{Height (m)}^2}$$

Each measurement of BMI will be converted to an age-and sex-appropriate standard deviation score (SDS), also referred to as a Z-score, by comparison with reference data available for average stature children from the Centers for Disease Control and Prevention (CDC).

The absolute values at Baseline, Week 26 and Week 52, and change from baseline at Week 26 and Week 52 will be summarized (n, mean, SD, median, 25th and 75th percentile, minimum, maximum) and presented by treatment group for both BMI and BMI Z-Score.

All assessments will be listed by treatment group, subject and visit.

14.5.4 Weight Z-Scores

Weight (kg) is measured at Screening, Day 1, Week 13, Week 26, Week 39, and Week 52. Each measurement of weight will be converted to an age-and sex-appropriate standard deviation score (SDS), also referred to as Z-score, by comparison with reference data available for average stature children from the Centers for Disease Control and Prevention (CDC).

The weight of the subject on Day 1 will be used as the baseline measure, regardless of whether this is recorded pre or post-dose.

The absolute values at Baseline, Week 26 and Week 52, and change from baseline at Week 26 and Week 52 will be summarized (n, mean, SD, median, 25th and 75th percentile, minimum, maximum) and presented by treatment group.

All assessments will be listed by treatment group, subject and visit.

**Study 111-301 Statistical Analysis Plan****14.5.5 Health-Related Quality of Life and Functional Independence**

The Health-Related Quality of Life (HRQoL) questionnaires and functional independence questionnaires are captured at Screening, Week 26 and Week 52. All summaries will be generated on the FAS.

Each table will include summaries of the absolute measures at each of these time points, and change from baseline at Week 26 and Week 52. The tables will be summarized by treatment group.

The statistical summaries will include the number of subjects with assessable data, mean, SD, median, 25th and 75th percentile, minimum and maximum. Subjects will not be included in a summary table if there is no baseline assessment available.

Separate summary tables will be provided for the total summary scores and the individual domains (scales). Individual questions (items) are not included in the summary tables.

Specific domains that are not considered clinically meaningful for the ACH indication are indicated.

Age defined versions within the same questionnaire will be summarized together. If a subject progresses during the course of the study from one age defined questionnaire to the next age defined questionnaire the results will be summarized together and the baseline assessment from the child's first questionnaire is referred to when summarizing change from baseline.

Self-reports and parent-reports will be summarized separately.

All subject data listings will include total scores, and domain (scale) scores.

14.5.5.1 Pediatric Quality of Life Inventory (PedsQL)

The PedsQL scales were designed to measure the core dimensions of health, as delineated by the WHO, as well as role (school) functioning. The following versions of the PedsQL are utilized in this protocol:

Parent/Caregiver Reported

- Parent Proxy-Report Children Ages 5-7
- Parent Proxy-Report Children Ages 8-12
- Parent Proxy-Report Adolescents Age 13-18

Self-Reported

- Child Self-Report Ages 8-12

Study 111-301 Statistical Analysis Plan

- Adolescent Self-Report Ages 13-18

The PedsQL consists of 4 scales of functioning (Physical, Emotional, Social, and School), which make up 3 summary scores.

Each of the items within a scale is scored as 0 (never a problem), 1 (almost never a problem), 2 (sometimes a problem), 3 (often a problem), to 4 (almost always a problem). Items are then reverse scored and linearly transformed to a 0-100 scale as follows: 0=100, 1=75, 2=50, 3=25, and 4=0.

Scales/Domains:

- Physical Functioning (8 items, min score=0, max score=800)
- Emotional Functioning (5 items, min score=0, max score=500)
- Social Functioning (5 items, min score=0, max score=500)
- School Functioning (5 items, min score=0, max score=500)

If at least 50% of items are completed within a scale, then the **mean score** is calculated for each scale using the transformed values:

$$\text{Scale/Domain Score} = \frac{\text{Sum of item scores}}{\text{Number of items answered}}$$

If more than 50% of the items are missing within a scale, then scale scores should not be calculated and be set to missing. (Varni, 1999)

For each of the scales, the mean scores (based on transformed values), and change from baseline at each scheduled visit, will be summarized (n, mean, SD, median, 25th and 75th percentile, minimum, maximum) by treatment group.

Summary scores:

In addition to the mean scale scores, the following summary scores will be calculated. All calculations use the transformed data.

- Psychosocial Health Summary Score (Sum of item scores/Number of items answered on Emotional, Social and School scales)
- Physical Health Summary Score (Sum of item scores/Number of items answered on Physical scale)
- Total Score (Mean Score, i.e., Sum of all items/Number of items answered on all scales)

For each of the above summary scores, the absolute values, and change from baseline at each scheduled visit, will be summarized (n, mean, SD, median, 25th and 75th percentile,

Study 111-301 Statistical Analysis Plan

minimum, maximum) and presented by treatment group. These scores are based on the transformed values.

Domain (scale) scores and summary scores will be listed by treatment group, subject and visit date.

14.5.5.2 Quality of Life in Short Statured Youth (QoLISSY)

The QoLISSY for parents, and the version for children and adolescents, consists of 22 likert-scaled items assigned to the core QoL dimensions: Physical, Social and Emotional, and 14 additional items in the dimensions Coping and Beliefs. In addition, the parent-reported version captures data on Future and Effects on parents.

The two versions of the questionnaire being used in this study are:

Parent/Caregiver Reported

- QoLISSY parent version for short stature (4-18)

Self-Reported

- QoLISSY child version (patient reported ≥ 8 years)

In both versions of the questionnaire, scoring is assigned to each individual item/question, according to whether the question is positively or negatively worded. Positively worded items are scored 1, 2, 3, 4, 5 (1: not at all/never, 2: very/very often, 3: moderately/quite often, 4: slightly/seldom, 5: extremely/always). Negatively worded items are reverse scored 5, 4, 3, 2, 1 (5: not at all/never to 1: extremely/always) so that a higher subscale score reflects higher quality of life.

Each of the questions are assigned to domains.

Domains

The following domains are common to both the parent and child versions of the QoLISSY:

- Physical (6 items)
- Social (8 items)
- Emotional (8 items)
- Coping (10 items)
- Belief (4 items)

The parent-report version contains additional items from two parent-only domains.

- Future (5 items)

Study 111-301 Statistical Analysis Plan

- Effects on parent (10 items, excluding growth hormone question.)

For each QoLISSY domain, the individual raw scores are summed to determine the raw domain total score. In order to calculate a domain score, 80% of the items must be completed (Bullinger 2015).

The QoLISSY raw domain total scores are then transformed to standard scores on a scale of 0-100 to allow for easier comparison from one measure to another. A score closer to 0 is indicative of poor quality of life and higher scores closer to 100 are indicative of a higher quality of life.

For each domain, the raw mean is transformed to a standard score as follows:

$$\text{Domain transformed score} = \frac{(\text{Raw Mean} - 1)}{4} \times 100$$

For each domain, the absolute values of the transformed scores, and change from baseline at each scheduled visit, will be summarized (n, mean, SD, median, 25th and 75th percentile, minimum, maximum) and presented by treatment group.

Summary Scores

The QoLISSY Total Score is calculated by summing the means in the physical, social, and emotional subscales and dividing by 3. The absolute value of the Total Score, and change from baseline at each scheduled visit, will be summarized (n, mean, SD, median, 25th and 75th percentile, minimum, maximum) and presented by treatment group.

Domain (scale) scores and summary scores will be listed by treatment group, subject and visit date.

14.5.5.3 Functional Independence Measure (WeeFIM)

The WeeFIM (Functional Independence Measure for children) instrument is a functional independence assessment tool that measures functional performance across three domains (self-care, mobility and cognition) from the caregiver's perspective.

Performance of a child on each of the individual items within the WeeFIM is assigned to one of seven levels on an ordinal scale that represent the function from complete and modified independence (levels 7 and 6) without a helping person to modified and complete dependence (levels 5 to 1) with a helping person.

If individual items (questions) within a domain are missing, the item result is imputed to 1, per guidance in The WeeFIM Clinical Guide v 6.49.

**Study 111-301 Statistical Analysis Plan**

If all items for a domain score are missing the domain score will be considered missing, and the Total score will not be calculated.

For each of the following domains and the total score, the absolute values at each scheduled visit, and change from baseline at each scheduled visit, will be summarized (n, mean, SD, median, 25th and 75th percentile, minimum, maximum) by treatment group:

- Self-care Score (min score=8, max score=56)
- Mobility Score (min score=5, max score =35)
- Cognition Score (min score=5, max score=35)
- Total WeeFIM rating (min=18, max=126)

Domain and total scores will be listed by treatment group and subject number.

Note: Although each domain will be summarized so that all aspects of this validated scale are reported, the cognition aspect of the WeeFIM (cognition subtotal score) is considered not to be of concern for subjects with achondroplasia.

14.6 Exploratory Endpoints

14.6.1 Sleep Study Scores

An optional sleep sub-study will be performed in a limited number of qualified sleep centers for a subset of subjects. A sleep-testing device will be used to assess the presence and severity of sleep-disordered breathing by measurement of blood oxygen saturation, pulse rate, and airflow during overnight monitoring. Sleep study data is collected at Screening, and Week 52.

Due to a small number of subjects enrolled in the optional sleep study (n=8) only listings of episodes of sleep apnea will be provided. These listings will include:

- Number of episodes of apnea per hour (Apnea Index).
- Number of episodes of hypopnea per hour (Hypopnea Index).
- Number of episodes /Duration of obstructive apneas
- Number of episodes /Duration of central apneas
- Number of episodes /Duration of mixed apneas
- Number of episodes /Duration of obstructive hypopneas
- Number of desaturations

All parameters collected in the sleep study will be listed.

**Study 111-301 Statistical Analysis Plan****14.7 Examination of Efficacy by Subgroups**

Subgroup analyses will be conducted on the primary and two key secondary efficacy endpoints, and will be based on the imputed data described for the primary analysis. Only subgroup categories with sufficient data will be analyzed. The ANCOVA model described in Section 14.3.2 will be applied separately for each category within a subgroup.

A Forest plot will provide an overall summary, and for each subgroup category, the difference between treatment group LS means (estimated as BMN 111-placebo), and the 95% confidence interval for the difference, at Week 52.

Subgroup categories of interest include:

- Sex (Male, Female)
- Age at Baseline (≥ 5 to < 8 , ≥ 8 to < 11 , ≥ 11 to < 15 , ≥ 15 to < 18 years)
- Tanner stage at Baseline (I, $>I$)
- Stratum (Male Tanner Stage I, Female Tanner Stage I, Male Tanner Stage $>I$, Female Tanner Stage $>I$).
- Baseline Height Z-Score (≤ -6 , > -6 to ≤ -5 , > -5 to ≤ -4 , > -4)
- Baseline AGV (≤ 3.5 , > 3.5 to ≤ 4.5 , > 4.5 cm/yr)

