14.6 Determination of Sample Size

With 55 subjects planned in each of the two randomized groups (one BMN 111 dose group and one placebo group), the power to detect a difference of 1.75 cm/year between the BMN 111 group and the placebo group in change from baseline in AGV at 12 months is approximately 90%, assuming that the pooled standard deviation of the change from baseline in AGV is 2.80, using a two-sided two-sample t-test at a 0.05 significance level. The power calculation is based on data from Study 111-202 (a phase 2, open-label, sequential cohort dose-escalation study) and Study 111-901 (a natural history study for pediatric subjects with achondroplasia).

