4.2 Study Design

Study 111-301 is a Phase 3 randomized, placebo-controlled, double-blind multicenter study to evaluate the effect of BMN 111 on growth in children with ACH. Subjects who are 5 to < 18 years old with documented ACH confirmed by genetic testing will have been enrolled in Study 111-901 (observational run-in study in pediatric patients with ACH) for at least a 6-month period immediately before study entry, and meet all study eligibility criteria.

Subjects who discontinue from the study drug will be encouraged to remain in the study and continue to undergo as many of the protocol-specified procedures and assessments as possible for the remainder of the study, as long as such continued participation does not detrimentally affect the health, safety, or welfare of the subject.

[figure not shown]
This 60-week study (up to 4 weeks of screening, 52 weeks of treatment with an additional 4 weeks of safety follow up) allows for assessment of the effect of daily BMN 111 administration on change from baseline in AGV, height, and body proportions in subjects treated with BMN 111 compared with control subjects in the placebo group. In addition, this study will help to further characterize safety and tolerability of BMN 111 in children with ACH.

At least 110 eligible subjects will be stratified based on sex and Tanner stage (Stage I, and > Stage I, with no more than 20% of subjects > Tanner Stage I) at Screening, and randomly assigned in a 1:1 ratio to one of two treatment groups: placebo or BMN 111 at 15 µg/kg. Approximately 33 clinical centers worldwide will participate in the study.

The 111-301 study design is presented below.

	Study 111-301 Statistical Analysis Plan
---	--

Figure 4.2.1: Study Design

Subjects who complete the 52 week treatment period in 111-301 study on randomized treatment, will be eligible to receive open label BMN 111 15 µg/kg daily in 111-302, to assess safety and efficacy of BMN 111 over the longer term. Subjects will have the option to enroll in 111-302 after the Week 52/Study Completion Visit. Week 52 assessments will serve as Baseline assessments for entry to study 111-302 if the visit occurs on the same day or within 2 weeks. Subjects who enroll into 111-302 more than 2 weeks after the 111-301 Week 52 visit will have a separate Baseline visit; the same assessments as those performed at Week 52 will be repeated at that time.

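### SAP 14.7 estimates no treatment-by-subgroup interaction, and its separate fits lose precision in the smallest categories

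*SAP*

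**What the plan says.** SAP 14.7 plans subgroup analyses of the primary and both key secondary endpoints on the imputed data. It names six factors: sex, age, Tanner stage, stratum, baseline height Z-score and baseline AGV. Together they have 2 + 4 + 2 + 4 + 4 + 3 = 19 categories. The ANCOVA of SAP 14.3.2 "will be applied separately for each category within a subgroup". The output is a forest plot of the BMN 111 minus placebo difference in LS means, with its 95% CI, for each category. Categories without sufficient data are left out, but no minimum size is given.

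The 14.3.2 model has main effects only: treatment, stratum, age, baseline AGV and baseline height Z-score. The only interactions named in either document are treatment-by-visit and subject-by-visit, in the repeated-measures and random-coefficients sensitivity models of Protocol 14.2.4. The Protocol synopsis allows subgroup analyses by Tanner stage or age but gives no method.

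SAP 4.2 enrols at least 110 children, "with no more than 20% of subjects > Tanner Stage I". SAP 14.1 makes every p-value outside the primary analyses of the three tested endpoints non-confirmatory.

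**The concern.** A subgroup display is read to see whether the effect differs between, say, prepubertal and pubertal children. That needs an estimate of the difference between category effects, with its uncertainty. The plan supplies only the within-category intervals, and comparing those by eye is a poor substitute: overlap or non-overlap of two intervals is not the contrast.

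The second issue is precision. A separate fit re-estimates the residual variance and three covariate slopes inside each category. That hardly matters in a category of 50 children. In one of about 11 it uses nearly half the information on those parameters alone. The small categories are also where a question about puberty or severity is most likely to arise.

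**Working it through.** **Inputs from the documents**
- Protocol 14.6: "With 55 subjects planned in each of the two randomized groups", a difference of 1.75 cm/year, and power of "approximately 90%, assuming that the pooled standard deviation of the change from baseline in AGV is 2.80". The test there is a t-test, two-sided at 0.05.
- SAP 4.2: children are "randomly assigned in a 1:1 ratio to one of two treatment groups", with Tanner >I capped at 20%. SAP 4.6.2: neither sex above 55%.
- SAP 14.3.2: the model terms listed above.

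The documents give no expected category sizes. Those below are assumptions, apart from what follows from the cap and the sex balance.

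**Step 1: the plan's own figure.** SE = 2.80 × √(2/55) = 0.534. Then 1.75/0.534 = 3.277, and power = Φ(3.277 − 1.960) = 0.906. The noncentral t with 108 df gives 0.901. The stated 90% reproduces. The plan states no figure for subgroups.

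**Step 2: size of the small strata.** 0.20 × 110 = 22 children above Tanner I at most, or 22/2 = 11 per sex if split evenly.

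**Step 3: degrees of freedom.** Within one stratum the stratum term is constant. The separate fit has an intercept, treatment and three slopes, so 11 − 5 = 6 df. A pooled stratum model has 4 category intercepts, 4 treatment effects and 3 common slopes, so 110 − 11 = 99 df. The t quantiles are 2.447 and 1.984, ratio 1.233. For Tanner >I as a whole (22 children) stratum still has two levels, so 22 − 6 = 16 df and 2.120/1.984 = 1.069.

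**Step 4: full width by simulation.** There were 4,000 runs per scenario, with N = 110, residual SD 2.80 in every category, common slopes for three covariates and no missing data. The separate fits omitted any remaining stratum term, which favours them slightly. The table gives mean 95% CI half-widths in cm/year.

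| Category size (scenario) | Separate | Pooled | Ratio |
|---|---|---|---|
| 88 (Tanner 88/22) | 1.21 | 1.20 | 1.01 |
| 55 (sex 55/55) | 1.55 to 1.56 | 1.52 | 1.02 to 1.03 |
| 44 (strata 44/44/11/11) | 1.76 | 1.69 | 1.04 |
| 22 (Tanner 88/22) | 2.69 | 2.40 | 1.12 |
| 11 (strata 44/44/11/11) | 4.89 to 4.95 | 3.40 | 1.44 to 1.46 |
| 10 (age 35/30/35/10, assumed) | 5.57 | 3.56 | 1.57 |
| 7 (strata 48/48/7/7, assumed) | about 13.6 | 4.31 | about 3.2 |

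Median half-widths give somewhat smaller ratios in the small cells: 1.38 to 1.40 at 11 and about 2.6 at 7.

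**Step 5: what an interaction could show.** SE = 2.80 × √(4/n₁ + 4/n₂), and power for 1.75 cm/year is Φ(1.75/SE − 1.96) plus a negligible opposite tail.
- Sex 55/55: SE = 1.068, power 37%. The interaction detectable with 80% power is 2.80 × 1.068 = 3.0 cm/year.
- Tanner 88/22: SE = 1.335, power 26%, detectable 3.7 cm/year.

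**Step 6: dependence on equal variance.** If a small category's true SD is k times the pooled SD, a pooled 95% interval covers about 2Φ(1.984/k) − 1. That is 89% at k = 1.25 and 81% at k = 1.5 (k is assumed). In the other direction, at n = 11 the separate interval becomes the narrower one when k is below about 1/1.45 = 0.69.

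**The case against.** The strongest case for leaving the section alone has four parts.

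- **The smallest cells may never appear.** The sufficient-data rule could remove the categories of 11 or fewer. This stands in part. Without a number, nobody can tell which categories it removes, and a removed category gets no estimate at all.
- **Heterogeneity can be read from the plot.** A reader might infer that effect modification cannot be assessed at all under this plan. The documents do not support that. Separate fits use different children, so the estimates are nearly independent and a rough contrast can be formed by adding variances. For Tanner stage, the half-widths in step 4 give √[(1.21/1.989)² + (2.69/2.110)²] ≈ 1.41 cm/year, close to the 1.33 in step 5. SAP 14.3.1 also plots AGV against age and Tanner stage. What remains is that the plan reports no such contrast, and a hand calculation is awkward for factors with three or four categories.
- **Separate fits are a legitimate choice.** A reader might infer that all the intervals are needlessly wide. They are not: the loss is trivial in large categories, and in small ones it depends on common slopes and variance. Pubertal and prepubertal growth may well differ in both, and step 6 shows the price of assuming otherwise. This stands, and it argues for adding an interaction model with unequal variances allowed, not for discarding the separate fits wholesale.
- **Interaction tests here are weak and numerous.** Six factors by three endpoints gives 18 tests. If they were independent, the chance of at least one false positive would be 1 − 0.95¹⁸ ≈ 60%. This stands as a reason to report estimates with intervals and to keep any p-value nominal.

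**Conclusion.** The point holds as a low-severity improvement. SAP 14.7 estimates effects within categories and no contrast between them, and neither document fills that gap elsewhere.

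The precision loss is confined to small categories that survive the sufficient-data rule. It is about 45% in mean width (23% from the t quantile alone) at 11 children, about 12% at 22, and 1 to 4% at 44 or more. The figure of 11 assumes N = 110, a filled 20% cap and an even sex split. The percentages assume common residual variance and common covariate slopes.

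A reader might also infer that the trial's conclusions are at risk. They are not: the subgroup results are non-confirmatory, and nothing here touches the primary or key secondary tests.

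**What to change.** For each subgroup factor, add to SAP 14.7 one ANCOVA on the full FAS with treatment, factor, treatment-by-factor and the primary covariates. Fit it to each imputed dataset and combine with PROC MIANALYZE where multiple imputation applies.

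- **Aliased terms.** Stratum already carries the sex and Tanner main effects. For sex, Tanner stage and stratum, keep stratum and add only the treatment interaction.
- **Variance.** Allow unequal residual variance by category in PROC MIXED where there is enough data.
- **Display.** Show the interaction estimate with its 95% CI on the forest plot, labelled non-confirmatory, with any p-value nominal.
- **Small categories.** Use this model's category contrasts there, and state the size below which that applies.
- **Reading.** Say in advance that a non-significant interaction is not evidence of a homogeneous effect.

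The cost is a paragraph of SAP text and one further model per factor and endpoint. No new data are needed and no alpha is spent. The price is the assumption of common covariate slopes in the pooled contrasts.
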